Subjects will practice applying the test material to their own limbs, following the procedure detailed in the Training Materials appendix, which a researcher will review for subjects before practice commences. That material explains, in simple language intentionally scripted as redundant (to emphasize the work's structure), the goals of this behavioral part of the study, describes the partnership between subject and technician in dosimetry data collection and details the procedures to be conducted.

10.3.3 Spray Sampling:

Spray Sampling is the procedure by which the spray is subsampled with patch dosimeters. Dosimeters of known surface area will be placed on subjects' limbs to intercept a portion of the spray applied to the arm. By weighing dosimetry patches before and after treatment, the mass of the intercepted material can be calculated. The spray delivery systems will also be weighed before and after each application.

Spray sampling will be conducted according to the procedure appended under Training Materials.

10.3.4 Lotion sampling:

The amount of lotion applied to limbs will be quantified in a series of 3 applications analogous to the Spray Sampling above. However, dosimeters are not required, nor are the extensive practice sessions. The amount applied is the weight difference in the dispensing tube before and after application.

10.3.5 Equipment Used to Assess Dosimetry Variables:

Passive dosimeters are 2.5-cm wide strips of Nexcare™ Co-Flex™ cohesive flexible bandage. They are applied to limbs in the manner of 'bracelets.'

Each test limb will be treated 3 times. Each subject will therefore use 12 bracelets per limb for dosimetry.

Bracelets will be weighed before and after treatment on a traceably calibrated Sartorius H51 balance (measurement increment 0.0001 g, 30 g capacity). Test material containers will be weighed before and after dispensing on a traceably calibrated Sartorius GC 2502 (measurement increment 0.001 g, 500 g capacity).

10.3.6 Repellency:

Before the repellent is applied, subjects will be guided to wash the lower arms with mild, low fragrance soap, rinsing them with a spray of ethyl alcohol (mixed with an equal part of water), and then drying them with a clean towel. A technician will then apply insect repellents to one forearm to give even, complete coverage of the skin on all sides of the arm. The treated area will extend a minimum of 10 cm along the forearm. The amount of repellent to be applied to any limb will be calculated in advance for each subject. The dosing rate will be the product of the subject's limb surface area multiplied by the grand mean (mean of all subject means) rate calculated in the dosimetry data analysis for that test material. Each subject will therefore be dosed at the same rate within a given repellent even if their individual application rates differed from the grand mean.

Three 'orientation' ink dots are arrayed longitudinally on both ventral forearms of each subject, at 3 cm intervals. On the treated arm (or treated portion of the arm if both arms are treated (see §8.3.2) the first dot is 3 cm distal to the treated area, the second dot marks the threshold of the treated area, and the third dot is 3 cm into the treated area. The untreated limb/limb portion has a spatially identical array of 3 lines for tick activity screening. The first dot, used for placement, insures that ticks are not placed within the treated area and so can detect a gradient of repellent density to which to orient. The second dot serves keep subjects aware of where the treated area begins and serves as a reorientation point for re-marking should either the first or the third dot become obscured.

We will employ a 15-minute exposure interval as a good minimum in terms of both the temporal resolution of the data set and subject ability to remain focused. Every 15 minutes, each subject selects an unused tick and tests it for active questing behavior as described. To initiate a screening or a repellent challenge, a tick is placed on the ventral arm or proximal palm, in the most hair-free portion, at the first (most distal line). Ticks are manipulated with the bristles of a fine artist's paintbrush. Ticks are placed so that they face the elbow. Ticks may be oriented to locomote toward the margin of the treated area with the gentle action of the paintbrush. Forearms should be held from approximately 30° to vertically above the lab bench surface if that increases the propensity of ticks to travel toward the body.

A crossing is scored if a tick travels at least 3 cm in a vector toward the elbow into the treated area (i.e., at least as far as the third line) within 3 minutes of beginning to move up the arm from the first line. A repulsion is scored when a tick changes its orientation away from, or parallel to, the margin of the treated area upon approach, or does not cross more than 3 cm toward the elbow within 3 minutes of entering the treated area.

Subgroups of approximately three subjects are led by a technician in the monitoring of time, ticks, and tick behavior. Time is monitored by referring to an electric chronometer with a highly visible display. The technician will record any crossings or repulsions as they occur. Repulsions are normally unambiguous reversals of direction. Subjects lift the tick off with the paintbrush after each assessment is complete. Any brushes that come into contact with a test material are discarded. Used ticks are immediately retired from the study by being transferred from the test arm to a container labeled "used".

Scientific Stopping Rule: Subjects are directed to cease tick exposures when a crossing is followed by another crossing within one-half hour, i.e., in either of the subsequent two exposure periods.

10.3.7 Forms for Retention of Source Data:

Dosimetry data will be recorded by a technician on a data form for each test formulation. Repellency data will be recorded by technicians on a repellency data form. Data forms are appended. The recording technicians sign and date the data forms.

10.4 Study Facility:

Data collection will take place in the main laboratory building and on the terrace of Carroll-Loye Biological Research in Davis, CA.

11 DATA ANALYSIS:

11.1 Experimental Unit:

The individual subject will be the experimental unit.

11.2 Replicates per Treatment:

For dosimetry, there will be 10 treated subjects. For efficacy testing, there will be 10 subjects treated with the test material and 2 serving as untreated controls, at each of 2 sites.

11.3 Statistical Methodology:

Statistics will be computed with SAS's JMP software, Version 5.0.1.2 (SAS Institute, Cary, NC).

11.3.1 Dosimetry:

Dosage will be calculated per square centimeter of skin. The amount of test material delivered to each dosimeter set in each trial will be calculated as:

weight after application – weight before application

The **total captured** by all treated dosimeters per trial will be calculated by adding the mass changes in all 4 dosimeters together, then subtracting or adding, respectively, any total weight gain or loss in the paired control dosimeters.

The **proportion covered** of the total limb surface area by the dosimeters is:

$$\frac{\text{Surface area of a set of 4 dosimeters}}{\text{Surface area of the limb}}$$

The estimated **dosage per trial** is:

$$\text{Total captured} \times 1/\text{proportion covered}$$

Subject means and standard deviations will be calculated for all measures of dosimeter weight changes as well as application behaviors (distance from nozzle to skin, number of pump actuations). We will use subject dose means for the test material to calculate the dosing grand mean (\pm SD). That mean, expressed as repellent weight per unit skin surface area, will be converted to volume and used to determine individual subject doses in the field repellency test. To accomplish that, the test material's specific gravity will be used to convert the dosage weight data to volumes, prepared for each subject on the basis of their skin surface area.

Subject effects on dosing behavior will be examined with nonparametric tests for n - sample independent cases (Kruskal-Wallis tests). In multiple regression analysis, the average amount of test material intercepted by each subject's dosimeters, as well as dosing per unit of skin surface area, will be examined in relation to the distance from nozzle to skin, limb size and the number of times the pump was actuated. The relationship between dosing behavior and dosage will also be examined with Spearman-rank correlation tests.

11.3.2. Repellency:

Because all subjects use different ticks, all ticks are used only once, and neither organism interacts directly with conspecifics at the level of the skin and the repellent during data collection, we will analyze data by subject as independent, replicated values. The hypothesis that the test materials will significantly reduce the number of ticks Crossing treated versus untreated skin is *not* the focus of this study. The focus is to compute, for each test material, a reasonable estimate of mean and standard deviation for the duration between application and sufficient repellency breakdown such that two ticks crossing on a subject within a half hour period. That pattern is here assessed at a resolution of 15 minutes.

Complete protection time (CPT) is measured as the length of time from initial application to the First Confirmed Crossing. A FCC is a Crossing followed by another Crossing within 30 minutes. For example, a Crossing at 90 minutes followed by another at 135 minutes is not confirmed, but a third Crossing at 150 minutes would confirm that at 135 minutes, giving a CPT of 135 minutes.

CPT measured in this way will yield a single time value for each subject. Mean CPT will be calculated across all 10 subjects per treatment, and will be presented with standard deviation and 95% confidence interval information as well.

Because all subjects serve as untreated controls to verify tick questing sufficiency, Relative Protection (RP) may also be calculated. Its utility is limited to the time period from first exposure until the first subject testing a given repellent is withdrawn by invoking the Stopping Rule (after which continued calculation of RP would likely bias its value in favor of repellency). Within that limit, RP evaluation provides complementary information when considering CPT. Such complementary information is important because it gives a rate function for performance the is intuitively explicable, and also because CPT is not currently discussed

in the draft EPA guidelines for tick testing. RP is calculated for each subject as a function of the total number of challenges in which ticks did not cross the barrier divided by the total number of challenges made. (Normally no ticks are repelled from the untreated controls.) Specifically, RP is the percentage prevented from crossing on the treated arm relative to the untreated arm, which is calculated as $\{[1 - (\text{Mean comparator}/\text{Mean Untreated})]100\}$ per unit time. Most simply, that time may be, e.g., per hour, with RP calculated for each hour as illustrated in the draft EPA guidelines of 12 June 2006. For each subject, cumulative RP may also be calculated for each time interval. This is the mean RP across all time intervals up to the selected point. In our design, Cumulative RP may be assessed at a maximum resolution of 15 minutes.

The decision to calculate means, standard deviations and 95% confidence intervals is based on the requirements for such estimates in the EPA draft repellent efficacy testing guidelines (1999; OPPTS 810.3700). While EPA staff have indicated at recent HSRB meetings that those guidelines remain under development, they are the de facto standards at present. Accordingly, despite stark statistical weaknesses in making such estimates for samples as small as, e.g., 6 subjects, for consistency with acting standards, we include them. Note that no normalizing data transformations are appropriate in their estimation. Further, as no statistical comparisons are planned, there are no other contexts for normalizing repellency data in the proposed study. To partially ameliorate the shortcomings, our chosen sample size is 10 subjects, which will improve precision in estimating product performance. This sample, which is larger than that traditionally required by US EPA, is implemented at considerable expense to the study sponsor, but is consistent with suggestions from HSRB advisors to EPA.

To further improve the utility of the data set, we propose to use Kaplan-Meier estimates of the survival function of repellency with time since application (Complete Protection Time). Kaplan-Meier analyses provide median estimates with substantially reduced error estimates compared to means and standard deviations; in particular, they are much

less sensitive to data censoring. Moreover, they do not rely on assumptions of data normality.' Combining a much larger sample with the Kaplan-Meier estimate of repellent survival improves our ability to estimate the true temporal performance function of test materials in the population

12 STUDY LOCATION(S):

Carroll-Loye Arthropod Behavior Laboratory at the letterhead address.

.

13 QUALITY ASSURANCE:

A separate, professional Quality Assurance Unit (QAU) will inspect the study. The QAU will report to the Study Director. Protocol Review and Comments must take place before data collection commences. In-Life Inspection must include observing the measurement and recording of key variables by subjects and researchers. In addition, the Final Report will be audited for completeness and accuracy. A QAU Statement will address compliance and noncompliance or any omissions in auditing. Findings from the In-Life Inspection and the Final Report, as well as the QAU Statement, will be transmitted to the Study Director and to the Sponsor Monitor.

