US EPA ARCHIVE DOCUMENT

COVER PAGE

EFFICACY TEST PROTOCOL SPC-002

©2007 by [name] [name].

EFFICACY TEST OF PICARIDIN-BASED PERSONAL TICK REPELLENTS

SYNOPSIS

Picaridin is a synthetic arthropod repellent developed as an alternative to DEET. Spectrum Division of United Industries Corp. proposes to replace all product performance studies for its Picardin-based repellents to bring them up to date with current Agency policy. In his letter dated 18 April 2007, [name] of the Agency's Registration Division spelled out the requirements to meet that goal. For a total of eight currently registered Spectrum products, efficacy testing will be conducted with three. Efficacy data from our tests of 7% Picardin Pump Spray will serve for that product and will also be adopted for 10% Pump Spray and Aerosol formulations, as well as for a 5.75% Towelette. Data from 15% Pump Spray will be used for that product as well as for 15% Aerosol and 12% Towelette. (Both Towelette formulations are simply the corresponding Pump Spray formula placed onto an inert fabric substrate.) The third test article is a 15% Picaridin Lotion formulated with sunscreen. It will be tested independently because interactions between repellency and sunscreen may make it substantively different from the other 15% formulations.

This protocol, dated 10 July 2007, was reviewed and approved by a private IRB, the Independent Investigational Review Board (IIRB), located in Plantation Florida, on 17 July 2007. The document in hand is that which IIRB reviewed, with the addition, on 17 July 2007, of the following elements for review by the United States Environmental Protection Agency, including its Human Studies Review Board: 1) This complete cover page; 2) the approved, signed Informed Consent Form, which replaces the proposed Informed Consent Form we submitted to IIRB; 3) record of PI-IIRB correspondence. The Table of Contents on the next page reflects those changes and additions.

EFFICACY TEST PROTOCOL SPC-002

©2007 by [name] [name].

EFFICACY TEST OF PICARIDIN-BASED PERSONAL TICK REPELLENTS

TABLE OF CONTENTS

Protocol	3
Protocol Approval Signatures	35
Appendices:	
Informed Consent and Subject's Bill of Rights	36
Sample data recording forms	46
Subject training documents	51
Materials Safety Data Sheets	57
IRB study set-up form	63
IRB site questionnaire	67
Record of PI-IRB correspondence	68

EFFICACY TEST PROTOCOL SPC-002

©2007 by [name] [name].

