The study-associated risks are of three types: exposure to test materials, exposure to biting arthropods and possible exposure to arthropod-borne diseases. As described below, subject health and safety are unlikely to be impacted by any participation-associated risks during or after the study.

The repellent's active ingredient has a low acute and chronic risk profile, a fact established through experimentation and through a history of consumer use. The concentrations of the active

ingredient in the products being tested are similar to those of other Picaridin products that EPA has recently registered. Subjects with known allergic reactions to insect repellents and common cosmetics are excluded from participating.

‘Repeat’ exposures during dosimetry are of brief duration before the product is washed off, and the likely total exposure time is much shorter than a typical single consumer application. Risks associated with inhalation and ingestion would only ensue from serious mishandling by subjects, a scenario that the study methods preclude.

While no bites are expected from the implementation of this protocol, it is worth noting that the testing will be conducted with laboratory ticks reared on quarantined rodents. The rodent hosts are screened to be pathogen-free for all tick-transmitted pathogens and hantavirus using appropriate culture, direct detection (PCR), and immunological screening assays.

In summary, the relatively benign quality of the repellents and the technical precautions we employ indicate that the chance that any subject will be at a health or safety risk is extremely small. If at anytime during the study a subject suffers a skin reaction or feels ill, he or she is instructed to inform the Study Director (i.e., the ‘Principal Investigator’), or anyone else who is also working to direct the study. Such subjects will be immediately withdrawn from testing and medical management will be implemented (§9.5). At least one qualified researcher will remain with the remaining test subjects if other researchers depart with an injured or ill subject. Subjects are clearly and repeatedly informed that they may remove themselves for any reason from the study at anytime, without penalty to their compensation.

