Balanced against these slight risks are substantial and reasonably likely benefits. The principal beneficiary will likely be the Sponsor, for whom new data and new labeling will meet current U.S. EPA registration standards. Spectrum is a major marketer of insect repellents in the U.S., primarily under the Cutter® label. Arthropod-borne disease is of growing significance in the U.S. and around the world where U.S. citizens are active. Moreover, discomfort associated with nuisance biting restricts many work and

pleasure activities. A test such as the one proposed here is the Sponsor's only legitimate path toward further product development and greater availability of new Picaridin-based tick repellents to U.S. consumers.

5.5 Standards Applied:

U.S. EPA Good Laboratory Practice Regulations (40 CFR 160); 40 CFR 26 subparts K and L; FIFRA §12(a)(2)(P); California State EPA Department of Pesticide Regulation study monitoring (California Code of Regulations Title 3, §6710).

6 INVESTIGATIONAL AND TEST MATERIAL CONTROL:

6.1 Test Substance:

6.1.1 Description of the Test Materials:

7% Picardin Pump Spray (data will also be bridged to 10% Pump Spray and Aerosol and 5.75% Towelette).

15% Picaridin Pump Spray (data will also be bridged to 15% Aerosol and 12% Towelette).

15% Picaridin Lotion formulated with sunscreen.

Note that the two Towelette formulations are simply the corresponding Pump Spray formulae placed onto an inert fabric substrate.

6.1.2 Dosage Form:

Lotion and liquid (Pump Spray) applied to the skin.

6.1.3 Trade Name:

Cutter.

6.1.4 Dose:

Determining dosage is part of this study's main objective. Dosage for repellency testing will be the mean of the subject means determined for each product in the dosimetry portion of this study. Dosage will be measured in weight and reported by weight and volume. Dosimetry data will be shared with the related repellent efficacy study detailed in the companion protocol SPC-001.

6.1.5 Manufacturing Site:

TBD

6.1.6 Test Material Storage During Study:

Prior to application, the test materials will be stored indoors, at room temperature and away from direct sunlight or direct sources of moisture, and according to any conditions specified by the Sponsor. Storage will be at Carroll-Loye Biological Research in Davis, CA.

6.1.7 Test Material Safety:

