EPA regulates use of inert ingredients (also termed "other" ingredients) by toxicology profiles in animal tests and by their inclusion in EPA lists of "approved" other ingredients. The insect-repellent products proposed for testing have been tested on animals for potential oral and dermal toxicity. The active ingredient (Picaridin) has an extensive toxicity data file, has been previously registered by EPA and has a positive safety record in consumer use. MSDS files for the products we propose to test are appended.

6.1.8 Test Material Composition and Stability:

The test material formulations are typical of topical cosmetics and insect-repellent products marketed to consumers. They will be produced under applicable Good

Laboratory Practice standards, with records available to EPA. They will be couriered to Carroll-Loye Biological Research, with Chain-of-Custody documented. After that, they will be stored at the Carroll-Loye offices in a closed cabinet at room temperature (approximately 19-27°C). The Sponsor believes that the formulations will be stable for the duration of the study, based on previously conducted storage-stability studies. The EPA has extensive experience with enforcing requirements for such tests based upon their history with similar products applied to humans. Spectrum intends to provide any requested information as appropriate to safety and efficacy issues.

6.2. Negative Control:

6.2.1 Description of the Negative Control:

The negative control is untreated for both dosimetry and repellency assays. Each subject simultaneously serves as a treatment and control subject.

6.2.2 Rationale for Employing a Negative Control:

Dosimetry testing requires an untreated control for the assumption that dosimeters will not gain appreciable weight from contact with untreated skin.

The 'negative control' for efficacy data sets serves to insure that each tick employed in the study is attracted to the test subject before it is used in a repellency challenge. Ticks that fail to meet the questing criterion (§8.4.1) are not used against Test Materials. In this way the negative control serves as a pre-screening of the ticks, such that only actively questing ticks are then exposed to the treatments. Based on this manipulation of a standard control design, the crossing rate on the negative control is judged to be 100%.

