- 9.1.2.1 Known to be phobic of ticks.

- 9.1.2.2 Known to be sensitive or showing sensitivity to any of the test product ingredients after application.
- 9.1.2.3 Poor physical condition.
- 9.1.2.4 Unwilling to submit to brief query about personal condition.
- 9.1.2.5 Use of insect repellent within 1 day preceding the study.
- 9.1.2.6 Unwilling to refrain from use of perfumed products, alcoholic beverages or smoking after 9 p.m. the evening preceding the test and throughout the test.
- 9.1.2.7 Known to be pregnant or lactating. Pregnancy will be self-checked by each female volunteer on the morning of the repellent test using an OTC test kit provided by Carroll-Loye. Results of each such test will be immediately verified by direct inspection by a technician trained to make that assessment. Only volunteers scored as nonpregnant will be allowed to participate.
- 9.1.2.8 Unable to deliver the test materials or nymphal ticks to own left and right arms.
- 9.1.2.9 Unable to see nymphal ticks on skin or otherwise effectively monitor them on skin.
- 9.1.3.10 Student or employee of the Study Director.

9.1.3 Number of Subjects and Rationale for Sample Sizes:

In both dosimetry and efficacy testing, we will engage 10 subjects per treatment. Each subject is a replicate. It is possible that a single set of 10 individuals could complete all parts of the study. It is much more likely that substantially more than 10 individuals will participate.

The number of subjects is chosen as a compromise between several conflicting factors. In the absence of clear means of estimating the distribution of outcome values, it is difficult to predict an ideal sample size. From a strictly scientific standpoint, an appropriate response under such circumstances would be to increase the sample size, but ethical and economic considerations demand the opposite in

the present study, particularly during the efficacy testing phase.

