All such potential participants are screened or re-screened for suitability for each test in a private, one-on-one conversation with the Study Director. Some former subjects have been excluded from repellent testing, for example, because they surpassed the upper age limit when the health risks from vector-borne disease statistically more serious. The Exclusion Criteria (see §9.1.2, above) are exercised by asking each candidate to address them in the interview with the Study Director. It is explained to female candidates that pregnancy will be assessed directly on the test day. The Study Director encourages candidates to ask questions and ask for clarification at any time during the interview and in all activities that follow. To candidates who pass screening, the Study Director describes the test's purpose, as well as necessary procedures and expected comportment, in plain language (in English). Candidates are then asked if they would like to retire from consideration. If they wish to remain in consideration, it is emphasized that they may withdraw from the test at any time during the test without penalty to their compensation. This freedom is especially re-emphasized in cases in which considerable effort or expense has been required to include a subject (e.g., travel to a distant site), to discourage the conception that that effort or expense creates any added obligation in the subject.

Candidates are given copies of the State of California Department of Pesticide Regulation *Experimental Subject's Bill of Rights* (appended) to read in the presence of Carroll-Loye personnel. They are also given a copy of the IRB-approved consent form to read. The amount and form of compensation are described. They are again encouraged to ask any questions about the test, which may include understanding its purpose more fully, understanding risks and discomforts more fully, and understanding treatment and compensation for injury more fully. While the majority of our subjects have worked with us on an occasional basis for a number of years, we encourage them to seriously evaluate their interests and concerns about participation each time. We ask them not to sign on immediately, but to give the situation due consideration (normally at least one day, sometimes less for those who have participated in multiple

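### The allergy exclusion stated in the risk section (§5.4) is not in the exclusion list put to candidates (§9.1.2), and the lotion's safety sheet that §6.1.7 says is appended is not there

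*Protocol*

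**What the plan says.** §5.4 (Balance of Risks and Benefits) describes the active ingredient as low risk and then adds: "Subjects with known allergic reactions to insect repellents and common cosmetics are excluded from participating". The same section concludes that the chance of harm to any subject is extremely small.

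The only item in §9.1.2 (Exclusion criteria) that deals with allergy or sensitivity is 9.1.2.2: "Known to be sensitive or showing sensitivity to any of the test product ingredients after application". On how the list is used, §9.1.5.3 (Screening of Candidate Subjects) says: "The Exclusion Criteria (see §9.1.2, above) are exercised by asking each candidate to address them in the interview with the Study Director".

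On the products, §6.1.7 (Test Material Safety) says: "MSDS files for the products we propose to test are appended". §6.1.1 names three test materials: a 7% pump spray, a 15% pump spray and the "15% Picaridin Lotion formulated with sunscreen". §6.1.8 adds: "The test material formulations are typical of topical cosmetics and insect-repellent products marketed to consumers".

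**The concern.** §5.4 describes a class-wide exclusion: anyone known to react allergically to repellents or ordinary cosmetics. §9.1.2 describes an ingredient-specific one. They select different people. The difference matters because many people know that a product gave them a reaction without knowing which component did. Such a person is out under §5.4 and in under §9.1.2.

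The IRB and the Agency read §5.4 as part of the risk assessment, while the site works from §9.1.2. If the two differ, the risk that was reviewed and the screen that is applied may not match. The wider class is relevant on the protocol's own account: §6.1.8 likens the test formulations to cosmetics and repellents on sale, and §9.5 has staff and subjects watch for allergic and irritant skin reactions.

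There is a secondary cost to the data. Under §9.5 a subject with a skin reaction stops at once. If that happens before a confirmed crossing, there is no observed complete protection time for that subject, while §11.3.2 plans a mean over all 10 subjects per treatment.

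The missing lotion sheet is a separate inaccuracy. It bears on the same screening step because it leaves the file with less ingredient information for one of the three products.

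**Working it through.** The plan states no figure on this point, so the check compares texts and counts documents.

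**1. The §5.4 exclusion against each item of §9.1.2.** The ten items, in paraphrase, are:
- fear of ticks
- sensitivity to ingredients of the test products
- poor physical condition
- refusal of a short query on personal condition
- repellent use in the preceding day
- refusal to abstain from scented products, alcohol and smoking
- pregnancy or lactation
- inability to place materials or ticks on the arms
- inability to see or follow the ticks
- being a student or employee of the Study Director (numbered 9.1.3.10 in the text)

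Items stating the §5.4 exclusion: 0 of 10. Items overlapping with it more narrowly: 1 (9.1.2.2).

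**2. A test case.** Take a candidate with a known reaction to another repellent or a cosmetic, cause unknown.
- Under §5.4: excluded.
- Under 9.1.2.2, known-sensitivity part: not excluded, since no sensitivity to a test ingredient is known.
- Under 9.1.2.2, part on sensitivity shown after application: excluded only after exposure and only if a reaction appears, whereas §5.4 speaks of not participating at all.
- Under the other nine items: not addressed.

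**3. Reach.** Three products at 10 subjects each give 3 × 10 = 30 efficacy places (§8.3.2) and 3 × 10 = 30 dosimetry places (§5.2, §9.1.3). One person may fill several. The lotion accounts for 10 + 10 = 20 of these 60 places.

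**4. The appended safety sheets.** By product and registration number:
- 7% pump (121-89): a test material
- 5.75% towelette (121-90): bridged only
- 15% aerosol, Outdoorsman (121-92): bridged only
- 15% pump (121-91): a test material
- 15% aerosol, Sport (121-92): bridged only
- 12% towelette (121-93): bridged only

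Six sheets; test materials covered: 2 of 3; lotion sheets: 0. The contents page starts "Materials Safety Data Sheets" at page 57 and the next appendix at page 63, so the section spans 63 − 57 = 6 pages for six sheets. A seventh sheet lost in reading is therefore unlikely.

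**5. What a lotion sheet would add.** The sheets list hazard ingredients, not full composition. Adding the percentages named on the two sheets for test materials:
- 7% pump: 7 + 30 = 37% named, 63% unnamed
- 15% pump: 15 + 35 = 50% named, 50% unnamed

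For the bridged products the named shares are 5.75 + 25 = 30.75%, 15 + 34 + 10 = 59% and 12 + 28 = 40%. Across all sheets, 41% to 69.25% is unnamed. A lotion sheet in the same format would help, but would probably not be a complete list for 9.1.2.2.

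**The case against.** The strongest reply is that the protocol has other ways to keep such a candidate out. §5.4 is itself protocol text, and §9.1.5.3 does not say that the §9.1.2 list is the only thing asked. Item 9.1.2.4 presupposes a query about personal condition, and the Study Director may refuse anyone. The consent form was not available to us and may mention allergy. This stands to a degree: a reader might infer that the site will not apply the safeguard, and the documents do not prove that. They show only that the stated and listed exclusions differ. None of these routes closes the gap in writing: the query's content is undefined, refusal is discretionary, and §9.1.5.3 gives the consent form to candidates who have already passed screening.

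A reader might also infer that 9.1.2.2 cannot be used for the lotion without its sheet. That does not follow. Observation after application needs no ingredient list, known sensitivity to picaridin or sunscreen can be asked about because §6.1.1 names both, and §6.1.8 says the sponsor will supply requested safety information.

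The synopsis says of the lotion: "It will be tested independently because interactions between repellency and sunscreen may make it substantively different from the other 15% formulations". That explains why its efficacy is tested separately. It is not a statement about allergy or hazard.

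On data loss, the plan has partial cover: three alternates (§9.1.7), who can replace subjects withdrawing before useful data exist, and Kaplan-Meier estimation where records are censored (§9.1.3, §11.3.2). In addition, §9.1.5.1 says first contact is with people who took part in earlier repellent tests, among whom known repellent allergy is plausibly less common.

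**Conclusion.** The point holds as two document defects. First, the allergy exclusion on which §5.4 relies is absent from §9.1.2 (0 of 10 items), and the narrower item there lets through a candidate whom §5.4 calls excluded. This concerns all 30 efficacy and 30 dosimetry places. Second, §6.1.7 is inaccurate for one of three test materials. That weakens screening under 9.1.2.2 for the lotion's 20 places without preventing it.

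The number of subjects who would be wrongly admitted cannot be estimated: the documents give no rate of cosmetic or repellent allergy in the volunteer pool, and people with some past reaction are not the same as people who would react to these products. The finding does not depend on such a number.

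The conclusion rests on reading §9.1.2 as the list that governs the interview, as §9.1.5.3 indicates, and on the appendix being complete at six sheets, as the contents page indicates. Neither defect changes how complete protection time is defined or analysed. Monitoring, stopping on reaction and an on-call physician on the testing day are already in §9.5. The matter should be settled before enrolment because it bears on subject safety and on what the reviewing bodies were told, but it ranks below a must-fix.

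**What to change.** Reconcile §5.4 and §9.1.2 before enrolment, so that the exclusion stated in the risk assessment and the one asked at interview are identical. Which wording to keep is for the investigator, the sponsor and the IRB to decide. If the narrower one is kept, §5.4 and the conclusion it supports need to be restated to match.

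Append the lotion's safety sheet together with its ingredient information, including the sunscreen, and have it available for 9.1.2.2 before any subject uses the lotion. If it cannot be appended, correct §6.1.7.

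The cost is about one line of text and one document that the sponsor should be able to supply. If the wider exclusion is adopted, an occasional volunteer may be turned away. The three alternates and the 58-person volunteer database give room for that.
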